## 7 Analysis of the primary endpoint

---

The primary endpoint, work absenteeism for any reason, will be reported as the average proportion of sick-days with standard deviation by treatment arm. It will be analysed as total counts (i.e. one observation per participant) using a Bayesian negative binomial regression with a fixed effect for BCG, hospital, enrolment week (categorical), age, department (whether planned to work on COVID-19 dedicated department), sick leave prior to enrolment (as a proportion of fte), and presence of at least one of four comorbidities: cardiovascular disease, use of anti-diabetic medication, asthma, pulmonary diseases. Age and prior sick leave will be modelled using a spline function. The total number of planned workdays for the respective person over the follow-up period will be used as offset (log-transformed). The brm function from the R package brms will be used for fitting the negative binomial model.

The effect will be reported as a relative risk with 95% and 99% CI. The posterior probability for the superiority hypothesis ( $RR < 1$ ) will be reported as well as the posterior probability for the futility hypothesis ( $RR > 0.8$ ).

Model assumptions will be checked using residuals plots and rootograms and posterior distribution plots will be presented. If model assumptions are violated, the following alternative model will be used: analysis as sick/non-sick working days (i.e. multiple observation per participant, one observation for each planned working day) using a Bayesian logistic regression model with a random intercept per participant, a fixed effect for BCG, hospital, observation week (categorical), age, department (whether planned to work on COVID-19 dedicated department), sick leave prior to enrolment (as a proportion of fte), and presence of at least one of four comorbidities: cardiovascular disease, use of anti-diabetic medication, asthma, other pulmonary diseases. Age and prior sick leave will be modelled using a spline function. An autocorrelation structure of 1st order over time within participants will be added. This model yields an odds ratio (OR) which can be interpreted as RR if the risk of sick leave is <10% and will be used for determination of superiority or futility in the same manner as planned for the RR.

The same modelling approach will be used during interim analyses. Please refer to section 10: Interim analysis for a description.

---

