## 10 Interim analyses

---

Interim analyses will be performed starting from 4 weeks after the first enrolled patient and subsequently every 2 weeks. The interim analysis will be performed by the trial statistician unblinded and will not be disclosed to other study team members. Monthly, the results will be provided to the DSMB unblinded. In case of suggested futility or efficacy, the DSMB statistician will independently replicate the full data analysis before drawing conclusions.

The disposition of participants and conduct of the study will be analysed and reported (section 5).

Of the baseline characteristics (section 6), the following will be reported during the interim analysis:

- Hospital of employment
- Age
- Gender
- History of BCG vaccination
- Department of employment
- Whether planned to work on COVID-19 dedicated department
- Position at department of employment
- Average number of working days in the hospital
- Total days of work loss due to illness between 1 January and 15 March 2020

The following endpoints will be analysed and reported in the same way as described in the above sections:

- Primary endpoint, work absenteeism for any reason (section 7). If during any of the interim analyses, the posterior probability of superiority is  $> 0.995$  or the posterior probability of futility is  $> 0.99$ , a conclusion is reached. In case of superiority, the trial will be stopped. In case of futility, the DSMB will take the totality of the data into account in their recommendation to continue or stop the trial.
- Hospital admission due to COVID-19 (section 8.13)
- SAEs and SUSARs (section 9.1)

Please also refer to the DSMB charter for roles and responsibilities and organizational aspects.

---

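### Does leaving a violated model assumption undefined in section 7 put the primary conclusion at risk?

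*SAP*

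**What the plan says.** SAP section 7 sets an order of models. The primary analysis is a Bayesian negative binomial regression on one count per participant. The check is named: "Model assumptions will be checked using residuals plots and rootograms and posterior distribution plots will be presented". Then comes the fallback clause: "If model assumptions are violated, the following alternative model will be used". The fallback is a Bayesian logistic model on planned working days, with its covariates, random intercept and first-order autocorrelation all listed. Its odds ratio "will be used for determination of superiority or futility in the same manner as planned for the RR".

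The rule extends to the interim looks. Section 7 says "The same modelling approach will be used during interim analyses", and section 10 says the primary endpoint "will be analysed and reported in the same way as described in the above sections". Looks start at week 4 and recur every 2 weeks. On who does this, section 10 says: "The interim analysis will be performed by the trial statistician unblinded and will not be disclosed to other study team members". Results go unblinded to the DSMB each month. Section 10 adds: "In case of suggested futility or efficacy, the DSMB statistician will independently replicate the full data analysis before drawing conclusions". Crossing the superiority limit (posterior probability above 0.995) stops the trial. Crossing the futility limit (above 0.99) leads only to a DSMB recommendation that weighs all the data.

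**The concern.** A graphical judgement with no stated limit selects the model that can end the trial. The person making it has the treatment codes and, from the second look on, has seen earlier estimates. The SAP does not say that fit is judged before the effect is seen, whether a switch carries forward to later looks, or that the replaced model is shown beside the fallback.

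If the choice of model followed the result, there would in effect be two chances of crossing 0.995 at each look. In the other direction, a switch could remove a crossing without triggering replication, because replication is tied to a suggested crossing. The stakes are the false-superiority rate, the power, and whether a stopping decision can be shown to be independent of the choice of model.

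**Working it through.** The SAP states no error rate or power for this rule, so there is no figure of its own to reproduce. The question is how far the model switch can move the chance of superiority.

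**From the SAP:** superiority limit 0.995; looks at week 4 and then every 2 weeks; two candidate models.

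**Assumed:**
- A flat prior, so that 0.995 corresponds to z = 2.576.
- An end at week 12, 26 or 52. The number of looks is (end − 4)/2 + 1, which gives 5, 12 or 25.
- Information that grows linearly with time.
- A correlation ρ of 0.83 to 0.95 between the two models' z-values. This comes from simplified fits to simulated trials without the covariates or autocorrelation.

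**One look.** If the better of the two models is always taken, P(superiority | no effect) = 1 − Φ₂(2.576, 2.576; ρ), where Φ₂ is the bivariate normal distribution function. With one fixed model this is 0.0050. With free choice it is 0.0068 at ρ = 0.95 and 0.0075 at ρ = 0.90.

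**Repeated looks.** Two correlated Brownian z-sequences were simulated under no effect, with 400,000 replicates. The entries are the chance of ever exceeding 2.576; ranges run over ρ.

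| Rule | 5 looks | 12 looks | 25 looks |
|---|---|---|---|
| Model fixed | 1.5% | 2.3% | 3.2% |
| One lasting switch, on fit only | 1.5–1.6% | 2.3–2.5% | 3.3–3.4% |
| Lasting switch steered by earlier looks | 1.8–2.0% | 2.8–3.2% | 3.9–4.5% |
| Favourable model always taken | 2.0–2.3% | 3.0–3.6% | 4.2–5.0% |

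A repeat run with a different seed agreed to within about 0.1 percentage point. If information saturates instead of growing linearly, the four 12-look figures are 1.6%, 1.6–1.8%, 2.0–2.3% and 2.1–2.5%.

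**Reading the table at 12 looks:**
- The rule as written (second row) adds at most 2.5 − 2.3 = 0.2 points.
- The extreme bound (fourth row) adds at most 3.6 − 2.3 = 1.3 points.
- Repeated looking with a fixed model already accounts for 2.3 − 0.5 = 1.8 points. That is a separate feature of the design.

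**The opposite direction.** Suppose the true effect gives the fixed model 80% power over 12 looks, and the analyst switches for good at the first look where the primary model crosses and the fallback does not. Power falls to 73–76%, a loss of 4 to 7 points. This requires someone to move away from success on purpose, and then to go unquestioned at each monthly DSMB report.

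**The case for a change.** The strongest case for a change is that three features combine: an ungraded visual trigger, repeated looks, and an analyst who knows the allocation. Replication happens only when a crossing is suggested, and it uses the same undefined criterion. Hiding only the current estimate would not fully help. At ρ = 0.83 and 12 looks, steering on earlier looks keeps (3.24 − 2.31)/(3.62 − 2.31) = 71% of the excess. The DSMB charter might cover some of this, but section 10 cites it as follows: "Please also refer to the DSMB charter for roles and responsibilities and organizational aspects". The rule for choosing the model belongs to the SAP.

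All of that is true of the text. It shows that the document alone cannot prove the model choice independent of the result. It does not show that following the plan gives a wrong answer. The instruction is to switch if assumptions fail, not if the estimate is unwelcome. There is one primary model, one named set of diagnostics and one fallback. Graphical checking without a numeric limit is ordinary practice. A switch would also be visible to the DSMB within a month, because an odds ratio would appear where a relative risk was expected.

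A tighter rule brings difficulties of its own. Different reasonable criteria, such as the count of zeros or the upper tail of the rootogram, need not agree. A ban on switching back could let one transient early flag displace the primary model for good. A second, blinded judge of fit would need interim outcome data that section 10 keeps from the rest of the team.

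One further point stands but is separate. The fallback's odds ratio is not on the same scale as the relative risk at the futility limit: RR 0.8 corresponds to a marginal OR of 0.792 at 5% risk. That concerns the fallback's scale, not its trigger. It leaves the superiority limit alone, since RR = 1 and OR = 1 coincide, and futility does not stop the trial automatically.

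**Conclusion.** The omission is real, but it is a gap that analysts fill sensibly. Used as written, the fallback rule changes the false-superiority chance by about 0 to 0.2 points (2.3% to 2.3–2.5% over 12 looks), and by similarly little at 5 or 25 looks. The larger figures, up to 3.6% at 12 looks and 5.0% at 25, are upper bounds that require result-driven choice. Nothing in the SAP invites that choice, and the monthly DSMB reports and the replication step work against it. A careful statistician would read the diagnostics before the treatment coefficient, note the reason for any switch, and show the negative binomial result beside the fallback. None of this needs an amendment.

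The conclusion depends on the assumed number of looks, flat prior, information curve and correlation, and on the fit check being made in good faith. The DSMB charter and the protocol were not available and could only add safeguards.

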## **2 Sample size determination**

---

The aim is to enrol a total of 1500 HCW (750 BCG and 750 placebo). For a detailed sample size calculation, please refer to the protocol.

---

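### In the fallback primary model, the participant-specific odds ratio is read as the relative risk, which overstates the effect and understates the futility probability; superiority is unaffected

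*SAP*

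**What the plan says.** SAP section 7 analyses total sick-day counts with a negative binomial model, planned workdays as offset, and reports a relative risk. Superiority is RR < 1 and futility is RR > 0.8. Descriptively, the endpoint "will be reported as the average proportion of sick-days with standard deviation by treatment arm".

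If the model assumptions are violated, the analysis moves to one record per planned working day, "using a Bayesian logistic regression model with a random intercept per participant" and a first-order autocorrelation structure. The SAP then states: "This model yields an odds ratio (OR) which can be interpreted as RR if the risk of sick leave is <10" per cent. It adds that this odds ratio "will be used for determination of superiority or futility in the same manner as planned for the RR".

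The rule reaches the interim looks: "The same modelling approach will be used during interim analyses". Section 10 sets the futility threshold at a posterior probability above 0.99 and sends unblinded results to the DSMB each month. Crossing it does not stop the trial automatically: "In case of futility, the DSMB will take the totality of the data into account in their recommendation to continue or stop the trial". No step in the SAP converts the fallback's odds ratio to a population relative risk.

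**The concern.** The 10% rule of thumb belongs to a logistic model without random effects. With a random intercept, the odds ratio compares the same participant under BCG and under placebo. The main model's RR, and the proportions reported by arm, compare averages over participants. These differ when participants differ in risk, even if the average risk is low, because much of the absence may come from a minority with high daily risk.

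Two results are at stake if the fallback is used: the effect size labelled as an RR, and the futility probability that the DSMB sees. The 0.8 margin would in effect become a different margin, set by a between-participant SD that nobody has specified. The main negative binomial model, with its log link, does not have this problem.

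**Working it through.** **Inputs.** From the SAP: the fallback model, the 10% rule, the cut-offs RR < 1 and RR > 0.8, the 0.99 threshold, and 1500 participants (750 per arm, section 2). Not in the SAP and therefore assumed over ranges: placebo-arm daily risk p0, random-intercept SD s (log-odds scale), and workdays per participant.

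**1. The SAP's rule where it does apply.** With no random intercept, RR = OR/(1 − p0 + p0·OR). For OR = 0.80:
- p0 = 2%: 0.80/0.996 = 0.803
- p0 = 5%: 0.80/0.990 = 0.808
- p0 = 9.9%: 0.80/0.980 = 0.816

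The rule is a fair approximation in that setting.

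**2. Direction with the random intercept.** A participant with placebo risk p has risk OR·p/(1 − p + OR·p) under BCG. For OR < 1 the denominator is at most 1, so this is at least OR·p. Averaging over participants gives RR ≥ OR for any distribution of p. For OR ≥ 1, RR ≥ 1 > 0.8. So every posterior draw with OR > 0.8 also has RR > 0.8, and P(OR > 0.8) ≤ P(RR > 0.8). Since OR < 1 exactly when RR < 1, P(superiority) is the same on both scales.

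**3. Size of the shift.** Average expit(a + ln OR + s·z) over z ~ N(0,1), with a solved so that the mean placebo risk equals p0. Population RR at a conditional OR of 0.80:

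| p0 | s = 0 | s = 1 | s = 1.5 | s = 2 | s = 3 |
|---|---|---|---|---|---|
| 2% | 0.803 | 0.808 | 0.817 | 0.830 | 0.860 |
| 5% | 0.808 | 0.817 | 0.831 | 0.847 | 0.877 |
| 9.9% | 0.816 | 0.831 | 0.847 | 0.864 | 0.893 |

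Conversely, at 5% risk a population RR of 0.80 would be reported as 0.792, 0.781, 0.765, 0.742 and 0.686 across the same SDs.

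**4. Effect on a posterior at the threshold.** Take 5% risk, s = 2 and a normal posterior for log RR centred at RR 1 with P(RR > 0.8) = 0.99. Its SD is 0.2231/2.326 = 0.0959. OR > 0.8 is the same event as RR > 0.847, so P(OR > 0.8) = Φ(0.1661/0.0959) = Φ(1.73) = 0.958. For s = 1 and s = 3 the values are 0.982 and 0.914.

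**5. Chance of crossing 0.99 at a single look when the true RR is 1.** SE(log OR) comes from the Fisher information of the random-intercept model with 750 per arm, a flat prior and a normal posterior. OR* is the odds ratio that gives a population RR of 0.80.
- RR scale: Φ(−ln OR*/SE − 2.326)
- OR scale: Φ(−ln 0.8/SE − 2.326)

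For 5% risk, s = 2 and 60 independent workdays, SE = 0.1236. RR scale: Φ(0.2984/0.1236 − 2.326) = Φ(0.09), about 54%. OR scale: Φ(0.2231/0.1236 − 2.326) = Φ(−0.52), about 30%.

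| 5% risk | s = 1 | s = 1.5 | s = 2 | s = 3 |
|---|---|---|---|---|
| 60 days, RR scale | 94% | 72% | 54% | 35% |
| 60 days, OR scale | 88% | 54% | 30% | 12% |
| 15 days, RR scale | 70% | 51% | 38% | 26% |
| 15 days, OR scale | 60% | 36% | 21% | 9% |

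The 15-day rows are a rough allowance for autocorrelation.

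**6. Simulation.** The random-intercept model was fitted to simulated trials of 1500 participants with 50 days each, 5% risk and a true population RR of 0.85 (40 trials per SD). Mean P(OR > 0.8) was 0.67 (s = 1) and 0.53 (s = 2), against mean P(RR > 0.8) of 0.76 and 0.71 from the same fits.

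**The case against.** - **Autocorrelation.** The SAP does not say how this term is parameterised. If it were a lagged outcome, the odds ratio would act on day-to-day transitions and the direction could reverse. With daily onset 1% and continuation 80%, an OR of 0.80 on both gives a prevalence ratio of about 0.68. This stands as a condition on the direction: the argument above takes the term as a latent error. That is the natural reading of an autocorrelation structure, and under the other reading the OR still would not be the RR.
- **Target.** The SAP never says that its relative risk is a population average. For a participant whose own risk is below 10%, an OR of 0.80 is an individual RR of at most about 0.816. But the main model's RR is a ratio of averages, and a low mean does not keep everyone below 10%. At 5% mean risk and s = 2, about 13% of participants exceed it and contribute about 68% of sick days.
- **Size.** No SD is given. The larger contrasts need a residual SD of 2 to 3 after adjustment for prior sick leave and the other covariates. At 5% risk and s = 1 the margin moves only to 0.817, of which 0.808 is the ordinary OR–RR gap. This stands.
- **Timing.** Early looks have less data. With 200 per arm and 15 days (assumed, 5% risk), the chances of crossing are 20 against 16% at s = 1 and 10 against 6% at s = 2, so the main effect may be a later futility signal. This stands too.
- **Consequences.** The fallback must first be triggered, futility is not binding, and the DSMB statistician replicates the analysis if futility or efficacy is suggested. Replication on the same scale would repeat the error, and where a futility signal is missed nothing prompts it.

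**Conclusion.** The concern holds. The rule as written does not fit the model it is attached to: within the fallback, the odds ratio overstates the population effect and the futility probability is understated. The direction needs no assumption about the shape of the random effects, only that the autocorrelation is not a lagged outcome. The size rests on assumed risk, SD and workdays. It is small for an SD up to 1 at risk up to 5%, and material from an SD of about 1.5. No claim is made about how the fallback's estimate compares with the negative binomial one.

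Importance is minor to moderate. It matters only if the fallback is used, futility is advisory, the superiority decision is unchanged, and no false efficacy claim results. It should still be corrected, because the reported RR and a stated decision margin would otherwise depend on an unspecified variance.

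**What to change.** Keep the fallback model and change what is taken from it. For each posterior draw, average the predicted probability of absence over participants, random effects (and any latent autocorrelation term) and planned workdays, once with everyone under BCG and once under placebo. The ratio is the population RR. Report it with its 95% and 99% credible intervals and apply RR < 1 and RR > 0.8 to it. Remove the sentence equating the odds ratio with the RR, and report the odds ratio only as a model parameter. State how the autocorrelation is parameterised. This works at any level of risk, so no 10% condition is needed.

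The cost is a short change to section 7 and modest post-processing of posterior draws at each analysis that uses the fallback, more if the autocorrelation is latent, and the same again in the DSMB statistician's replication. No new data are needed. Fixing it in advance avoids choosing the scale after seeing results.

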## **8 Analysis of the secondary endpoints**

---

### **8.1 number of days of unplanned absenteeism, because of COVID-19 disease**

The same modelling approach will be used as for the primary endpoint.

### **8.2 Cumulative incidence of COVID-19 disease**

This will be analysed as time-to-event outcome. A proportional hazards model will be used, adjusted for hospital, enrolment week (categorical), age, department (whether planned to work on COVID-19 dedicated department), sick leave prior to enrolment (as a proportion of fte), and presence of at least one of four comorbidities: cardiovascular disease, use of anti-diabetic medication, asthma, other pulmonary diseases. Age and prior sick leave will be modelled using a spline function. When applicable (i.e. in the event that one or more participants have died during the follow-up period) a competing events analysis will be performed in addition (Fine & Gray model).

### **8.3 Cumulative incidence of self-reported acute respiratory symptoms or fever**

Same analysis as 8.2 Cumulative incidence of COVID-19 disease.

### **8.4 Cumulative incidence of hospital admission due to COVID-19 disease**

Same analysis as 8.2 Documented infection with SARS-CoV-2.

### **8.5 Cumulative incidence of intensive care admission due to COVID-19 disease**

Same analysis as 8.2 Documented infection with SARS-CoV-2.

### **8.6 Cumulative incidence of death due to COVID-19 disease**

Same analysis as 8.2 Documented infection with SARS-CoV-2. If deaths not due to documented SARS-CoV-2 infection have occurred, this will be considered a competing event.

---

## 9 Analysis of the exploratory endpoints

---

### 9.1 Safety endpoints: (Serious) adverse events (AE / SAE) and suspected unexpected serious adverse reactions (SUSAR)

Frequencies of AEs, SAEs and SUSARs will be described per intervention arm for total number of events, per solicited event, and for unsolicited events. Frequencies of having at least one AE / SAE / SUSAR will be compared using logistic regression analysis and reported as OR with 95% CI.

For the following endpoints, the same modelling approach will be used as for endpoint 8.2 Cumulative incidence of COVID-19 disease:

- 9.1.1 the cumulative incidence of hospital admission for any reason
- 9.1.2 the cumulative incidence of intensive care admission for any reason
- 9.1.3 the cumulative incidence of death for any reason

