### 3.1 Treatment groups

BCG: participants randomised to receive BCG

Placebo: participants randomised to receive placebo

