### 3.2 Analysed populations

The primary analysis population is the intention-to-treat (ITT) population in which participants will be analysed according to the random allocation.

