### 4.2 Handling of missing data

For analyses of primary or secondary endpoints with missing data, multiple imputed data analysis will be performed using Multivariate Imputation by Chained Equations; complete data analysis will be performed as a sensitivity analysis to check for inconsistencies. Missing outcome data will not be imputed.

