### **5.1 Participant disposition and size of the analysed populations**

The study flowchart will describe:

- Number of subjects screened
- Number of subjects not meeting the eligibility criteria
  - o Reasons for non-eligibility
- Number of subjects eligible but not included
  - o Reasons for non-inclusion
- Number of participants included and randomised
- Early termination: Number of participants withdrawn, dropouts
  - o Reasons for early termination

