### **5.2 Conduct of the study**

The following will be reported on the conduct of the study:

- Enrolment period: date First Patient First Visit – date Last Patient First Visit
- Distribution of actual duration of follow-up per participant by treatment arm
- Number and proportion of days with missing outcome measurement by treatment arm

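### The SAP section 9.1 comparison of participants with at least one AE, SAE or SUSAR ignores follow-up time; a minor weakness, easily removed for SAEs by using the section 8.2 model

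*SAP*

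**What the plan says.** Section 9.1 describes AE, SAE and SUSAR frequencies per arm and then specifies the comparison: "Frequencies of having at least one AE / SAE / SUSAR will be compared using logistic regression analysis and reported as OR with 95% CI". It names no exposure term, censoring rule, observation window or analysis set.

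The same section then sends hospital admission, intensive care admission and death for any reason to a different method: "For the following endpoints, the same modelling approach will be used as for endpoint 8.2 Cumulative incidence of COVID-19 disease". Section 8.2 describes that method: "This will be analysed as time-to-event outcome. A proportional hazards model will be used, adjusted for hospital, enrolment week (categorical), age".

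Unequal follow-up is expected. Section 5.1 lists "Early termination: Number of participants withdrawn, dropouts", and section 5.2 lists "Distribution of actual duration of follow-up per participant by treatment arm".

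Section 10 starts interim analyses 4 weeks after the first enrolment and repeats them every 2 weeks, with results to the DSMB monthly. SAEs and SUSARs are analysed there as in section 9.1.

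On missing data, section 4.2 says: "Missing outcome data will not be imputed". On groups and populations, section 3.1 has "BCG: participants randomised to receive BCG" (and the same for placebo), and section 3.2 has "The primary analysis population is the intention-to-treat (ITT) population in which participants will be analysed according to the random allocation".

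**The concern.** An ever/never outcome has a clear meaning only if everyone is observed for the same period. Here a participant seen for one week and a participant seen for the whole study would contribute equally to the SAE comparison. Admission and death for any reason, which overlap heavily with SAEs, are analysed with follow-up time in the same section. Two closely related sets of serious events could therefore respond differently to the same withdrawals.

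Two things are at stake. First, if one arm loses more participants than the other, its SAE frequency is understated and the OR moves in its favour. Second, at interim looks the percentage with an SAE depends on how recently people enrolled, so a DSMB cannot read it as a risk or compare it from one look to the next.

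**Working it through.** The SAP states no event rate, withdrawal rate or follow-up length, so there is no planned figure to reproduce. All rates below are assumptions, and a constant hazard is assumed throughout.

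**1. Rare events, person-time only.** If a fraction *a* leaves at mid-study in one arm and *b* in the other, mean follow-up is 1 − a/2 and 1 − b/2 of the full period. With no true difference, the crude risk ratio is distorted by (1 − a/2)/(1 − b/2). With a = 5%:
- b = 10%: 0.975/0.950 = 1.026
- b = 15%: 0.975/0.925 = 1.054
- b = 20%: 0.975/0.900 = 1.083

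**2. The OR itself, no true difference.** Take a full-period risk of 2%. The half-period risk is 1 − √0.98 = 0.01005. Score those without a recorded event as having none.
- Placebo, 5% leaving: 0.95 × 0.02 + 0.05 × 0.01005 = 0.01950
- BCG, 10% leaving: 0.90 × 0.02 + 0.10 × 0.01005 = 0.01901, OR 0.974
- BCG, 20% leaving: 0.80 × 0.02 + 0.20 × 0.01005 = 0.01801, OR 0.922

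At full-period risks of 10%, 30% and 60% the ORs are 0.972, 0.967 and 0.953 (5% v 10%), and 0.918, 0.904 and 0.867 (5% v 20%).

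**3. The other reading of section 4.2.** Suppose instead that people who leave without an event are dropped as missing. Those who had an event before leaving stay in. At 2% risk, the odds are then:
- Placebo, 5% leaving: 0.01950/(0.95 × 0.98) = 0.02095
- BCG, 10% leaving: 0.01901/(0.90 × 0.98) = 0.02155, OR 1.029
- BCG, 20% leaving: 0.01801/(0.80 × 0.98) = 0.02297, OR 1.097

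The shift is of similar size in the opposite direction, so dropping them does not remove the problem.

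**4. Equal follow-up.** With no true difference, the OR stays at 1.000 when both arms lose 5%, when both lose 20%, or when entry is staggered uniformly in both. With a true hazard ratio of 1.5 and staggered entry, the OR moves from 1.508 to 1.503 at 2% risk, from 1.541 to 1.513 at 10%, and from 1.651 to 1.542 at 30%. Attenuation is negligible for rare SAEs.

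**5. Interim percentages.** If enrolment is uniform and still running, mean follow-up is about 4/2 = 2 weeks at the week-4 look and 8/2 = 4 weeks at week 8. If enrolment stopped at week 4, it is 2 + 4 = 6 weeks at week 8. With a rare event and an unchanged hazard, the crude SAE percentage therefore doubles or triples between these looks because of enrolment pace alone.

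**The case against.** A reader might go further and infer that the comparison covers everyone randomised and that early leavers, people never injected and recent enrollees are counted as event-free for the whole study. The SAP does not support this. Section 9.1 names no population and no coding rule, section 3.2 presents ITT as the primary analysis population, not the only one, and section 4.2 could be read against scoring unobserved follow-up as no event. Events before withdrawal still count. People never injected can still report AEs; including them would be a question of analysis set, not of follow-up. Nothing in the SAP mentions anyone receiving the wrong product. A safety set may be defined in the protocol.

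Four further arguments limit the point:
- The endpoints in 9.1 are listed as exploratory, and no decision rule depends on this OR.
- The most important serious outcomes already have a time-to-event analysis.
- Section 10 also calls for the section 5 reports, so the DSMB will see follow-up by arm next to the SAE figures.
- The shift is small against sampling error. With 750 per arm and an assumed 2% risk (15 v 15 events), the standard error of the log OR is √(2/15 + 2/735) = 0.369, which gives a 95% interval of about 0.49 to 2.06.

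All of this stands as a limit on severity. It does not justify the method: showing follow-up by arm lets a reader see an imbalance but does not correct the OR, and neither reading of section 4.2 gives a sound comparison when withdrawal differs.

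**Conclusion.** The point holds in a limited form, and its severity is minor. Section 9.1 specifies a comparison that cannot use follow-up time in a trial where the SAP itself expects follow-up to vary, while a suitable model is already applied to neighbouring endpoints.

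The bias needs withdrawal that differs between arms. Under the assumed 5% versus 10% to 20% leaving at mid-study, a constant hazard, rare events, and participants without a recorded event scored as having none, it is about 3% to 8% in favour of the arm with more withdrawals. Nothing in the SAP shows that such an imbalance is expected. With equal follow-up or balanced staggered entry, the OR is unbiased at the null.

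The gain from changing is protection against unequal withdrawal and interim SAE figures that can be interpreted.

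**What to change.** In section 9.1:
- Analyse time to first SAE, censored at withdrawal or data cut, with the section 8.2 model or an unadjusted version if events are few.
- At interim looks, report SAEs per person-time by arm.
- Keep logistic regression for solicited AEs, over a fixed window after injection that is stated or cross-referred to the protocol.
- As a clarification only, state the safety analysis set or refer to the protocol for it.

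The cost is a few lines of SAP text and little programming. Endpoints 9.1.1 to 9.1.3 already require entry and censoring dates. The SAE onset date is needed in addition; the SAP does not say whether it is recorded, so this should be confirmed. The SAE effect measure becomes a hazard ratio or rate ratio instead of an OR. Censoring also assumes that withdrawal is unrelated to later SAE risk, so reasons for withdrawal by arm should be read alongside the result.
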